**An Investigator-Initiated Study To Evaluate Ara-C and Idarubicin in
Combination with the Selective Inhibitor Of Nuclear Export (SINE)
Selinexor (KPT-330) in Patients with Relapsed Or Refractory AML**

Study code: SAIL

Phase II study

STATISTICAL ANALYSIS PLAN

Signatures:

Statistical Analysis Plan was prepared by:

[name]
Study Statistician
4Pharma Ltd

Date

Statistical Analysis Plan was reviewed/approved by:

[name]
Senior Statistician
4Pharma Ltd

Date

[name]
Responsible person from the Sponsor
GSO

Date

[name]
Principal Investigator

Date

Table of Contents

1	Abbreviations.....	4
2	Study objective(s)	4
3	Design and type of the study.....	5
4	Study variables.....	5
5	Sample size considerations.....	5
6	Statistical hypotheses.....	6
7	Analysis sets	6
7.1	Intention-to-treat (ITT) set	6
7.2	Per protocol (PP) set	6
7.3	Safety set	6
8	General statistical considerations	6
9	Demographic and other baseline characteristics.....	7
10	Concomitant medication/treatment	7
11	Extent of exposure and compliance	7
12	Analysis of efficacy	7
12.1	Primary efficacy variables	7
12.2	Secondary efficacy variables	8
12.3	Additional analyses	8
13	Analysis of safety	8
13.1	Adverse events	8
13.2	Laboratory safety variables.....	9
13.3	Other safety variables	9
14	Completion and premature discontinuation	9
15	Deviations from the analyses planned in the study protocol	9
16	Execution of statistical analyses.....	9
17	Hardware and software.....	9
18	References	9
19	Appendices	9
19.1	Schedule of assessments.....	10
19.2	Table and figure plan.....	13

1 Abbreviations

AE	Adverse event
AML	Acute myeloid leukemia
ATC	Anatomical Therapeutic Chemical
CI	Confidence Interval
CR	Complete Response
CRi	Complete Response with incomplete blood recovery
CTCAE	Common Terminology Criteria for Adverse Events
ECOG	Eastern Cooperative Oncology Group
EFS	Event-free-survival
GFR	Glomerular filtration rate
ITT	Intent-to-treat
KM	Kaplan-Meier
OS	Overall Survival
RFS	Recurrence-free-survival
SAE	Serious adverse event
SCT	Stem Cell Transplant
PP	Per-protocol

2 Study objective(s)

The primary objective is to determine the efficacy of Selinexor in patients with relapsed/ refractory AML by complete response rate (CR or CRi), as defined by the revised recommendations of the International Working Group for diagnosis, standardization of response criteria in Acute Myeloid Leukemia for AML (Cheson et al 2003).

Secondary objectives of the study are 1) To determine the efficacy of Selinexor in combination with standard chemotherapy in patients with relapsed/ refractory AML by:

- Rate of partial remissions
- Percentage of patients being transplanted after induction therapy
- Early death rate
- Overall survival (OS)
- Event-free survival (Events are defined as Death, not achieving a CR or CRi, Relapse after CR or CRi) and

2) To evaluate overall safety and tolerability of Selinexor.

3 Design and type of the study

This is a phase II non-randomized, single-arm, open-label, multicentre study in patients with relapsed or refractory AML.

4 Study variables

The following variables will be evaluated.

The demographic and baseline variables:

Gender, age, race, details on leukemia diagnosis, prior therapy, medical history, current symptoms and residual toxicities from prior therapies, ECOG performance status, clinical neurological examination, cardiac evaluation, disease status, concomitant medication, prior transplantation, primary or secondary AML, early/late relapse from first therapy, mutation, karyotype risk category.

The primary efficacy variable:

The rate of complete responders according to the Cheson criteria.

The secondary efficacy variables:

Rate of partial remissions, percentage of patients being transplanted after induction therapy, early death rate, Overall survival (OS), Event-free survival (EFS), Recurrence-free-survival (RFS)

The safety variable:

Adverse events (AE), blood pressure, pulse, temperature, physical examination, urine analysis, hematology, clinical chemistry, coagulation tests.

5 Sample size considerations

The sample size calculation is based on the evaluation of response rates according to Fleming using the A'Hern extension (Sample size tables for exact single-stage phase II designs. Statist. Med. 2001;20:859-866). In Fleming's procedure to response levels p_0 and p_1 are specified, where p_0 is the largest proportion of responders, which would clearly imply that the treatment does not warrant further investigations and p_1 the minimum required proportion of responders that would imply that the treatment warrant further investigations. The following characteristics were specified in the sample size calculation:

- $p_0 = 0.30$
- $p_1 = 0.60$
- $\alpha = 0.05$ (one-tailed) and
- $\beta = 0.10$

The sample size calculation ended up in 25 patients to be recruited to ensure a power of 90 % for the discrimination of p_0 and p_1 . In addition, 15 additional patients were submitted to an adapted drug regimen (flat dose 60mg of Selinexor instead of 40 mg /m² of Selinexor). Using a similar approach, the power will be 80 % to discriminate a $p_0=30$ % from a $p_1=65$ %, with a one-tailed α of 0.05 %.

6 Statistical hypotheses

The purpose of this study is to evaluate efficacy of Selinexor in patients with relapsed/ refractory AML by complete response rate (CR or CRi). The null-hypothesis to be tested is

H_0 : *The observed response rate is less or equal than 30 %*

against the alternative hypothesis

H_1 : *The observed response rate is over 30 %*

7 Analysis sets

A detailed subject classification document will be prepared in a Data Review meeting prior database lock. The document will assign patients to the respective analysis sets depending on the observed protocol violations.

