8.2 Sample Size Calculation

The sample size calculation is based on the evaluation of response rates according to Fleming using the A'Hern (Sample size tables for exact single-stage phase II designs. Statist. Med. 2001;20:859-866.) extension.

In Fleming's procedure two response levels p_0 and p_1 are specified:

- the largest response proportion p_0 which, if true, would clearly imply that the treatment does not warrant further investigations (except for other types of administration, e.g. in standardized combinations); and
- the minimum required response level p_1 that would imply the treatment warrants further investigations.

The following characteristics were specified

- $p_0 = 0.30$
- $p_1 = 0.60$
- $\alpha = 0.05$ (one-tailed) and
- $\beta = 0.10$

$N=25$ patients should participate in the study to ensure a power of $1-\beta=0.90$ for the discrimination of p_0 and p_1 . According to Fleming the null hypothesis should be rejected if at least

$$r = \left\lceil Np_0 + Z_{1-\alpha} \sqrt{Np_0(1-p_0)} \right\rceil + 1$$

responses are observed (x^* denotes the nearest integer to). With p_0 and N defined as above and $Z_{1-\alpha} = (1 - \alpha)$ -quantile of the normal distribution = 1.645 at least 12 responders should be observed to show the efficacy as postulated.

Using the same approach in the 15 additional patients, submitted to an adapted drug regimen, the power will be 80% to discriminate a $p_0=30\%$ (expected CR rate) from a $p_1=65\%$ (meaningful increase in CR rate), if 8 out of 14 completed patients are considered as responders, with a one-tailed alpha error of 5%.

Alternatively, the power will be 90% to discriminate a $p_0=30\%$ from a $p_1=70\%$ again if 8 out of 14 completed patients are considered as responders, with a one-tailed alpha error of 5%.

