7.3 Safety set

The Safety set will comprise all subjects who received at least one administration of the study medication at any dosage and who have a subsequent safety measurement available.

8 General statistical considerations

The aim of the study is to evaluate the effect of Selinexor in patients with relapsed / refractory AML by complete response rate (CR or CRi).

All background, primary and secondary efficacy variables, and safety variables will be summarized by visit and treatment group. In addition to absolute values, changes from baseline values will be summarized, if feasible.

Summary statistics will include at least the number of patients, mean, standard deviation, median, minimum and maximum for continuous variables, and frequencies and percentages for categorical variables. The results of statistical tests (including 95% CIs) will be included in the tables, when appropriate.

If the assumptions of the parametric statistical test are not met, the use of common transformations (e.g. logarithmic, square root) will be considered. Appropriate non-parametric methods will be used if normality assumptions are not met even after transformations.

In the statistical analyses a p-value less than 0.05 will be considered as statistically significant. If not stated otherwise, all tests will be performed as two-sided and two-sided 95% CIs will be produced for the treatment differences. No adjustments for the p-values will be made. Missing values will not be imputed in the analyses.

Subgroup analyses by dosing schedule (Selinexor / mm² vs. flat dose of Selinexor) will be conducted for all study data.

The table and figure plan is presented in Appendix 18.2.

9 Demographic and other baseline characteristics

All background and other baseline characteristics will be tabulated with descriptive statistics. Medical history and other medication will be summarized with frequency distributions. Tabulations will be conducted overall and by dosing schedule. No statistical tests will be carried out for any baseline measures between the dosing schedules.

10 Concomitant medication/treatment

Concomitant medication and treatments will be summarized overall and by dosing group using ATC classification.

11 Extent of exposure and compliance

The extent of exposure and treatment compliance will be summarized descriptively overall and by dosing schedule.

12 Analysis of efficacy

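### SAP section 5 prints the second cohort's one-tailed alpha as 0.05 % where the protocol has 5 %, and the stated 80 % power cannot hold at the printed level

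*SAP*

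**What the plan says.** SAP section 5 first sets out the design for 25 patients (30 % against 60 %, one-tailed alpha 0.05, beta 0.10). It then says that "15 additional patients were submitted to an adapted drug regimen" and that "the power will be 80 % to discriminate a" 30 % from a 65 % response rate, "with a one-tailed α of 0.05" followed by a per-cent sign. It gives no responder cut-off and no number of completed patients for this cohort.

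Protocol section 8.2 makes the same 80 % claim for 30 % against 65 %, conditional on a count rule: "if 8 out of 14 completed patients are considered as responders, with a one-tailed alpha error of 5" per cent. The protocol synopsis repeats this.

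Two other parts of the SAP bear on the point. Section 8 states: "In the statistical analyses a p-value less than 0.05 will be considered as statistically significant", with tests two-sided unless stated otherwise. Section 12.1 reports the response rate with a 95 % Wilson score interval, overall and separately by dosing schedule.

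**The concern.** Read literally, 0.05 % is 0.0005, one hundredth of the protocol's 5 %. The SAP therefore pairs a power of 80 % with a type I error at which so small a cohort could not reach that power. The SAP also leaves out the 8-of-14 rule, so a reader who has only the SAP cannot recover the intended criterion from section 5.

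What is at stake is the accuracy of a stated error rate. A study report that takes its design paragraph from SAP section 5 would give an alpha that contradicts the protocol and a power that does not follow from it. SAP section 15, which lists deviations from the protocol, mentions only the clarified hypothesis, and the 2018 addendum leaves the sentence as it stands.

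**Working it through.** **Inputs.** p0 = 0.30 and p1 = 0.65 (protocol 8.2 and SAP 5); p1 = 0.70 as the protocol's alternative; n = 14 completed patients and r = 8 (protocol 8.2); n = 15 (SAP 5); alpha = 0.05 (protocol) or 0.0005 (SAP as printed).

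**Method.** Both documents cite the exact single-stage extension of Fleming's design. Take the smallest r with P(X ≥ r | n, p0) ≤ alpha. Power is then P(X ≥ r | n, p1), where P(X ≥ r | n, p) = Σ from k = r to n of C(n,k) p^k (1−p)^(n−k).

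**Step 1: the protocol's figures.** With n = 14 and r = 8, the attained alpha is 0.0315. Power is 0.816 at 65 % and 0.907 at 70 %. The protocol's 80 % and 90 % both reproduce. The smallest exact design at 5 % for either claim is 14 patients with a cut-off of 8.

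**Step 2: the SAP's alpha as printed.**

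| n | r | P(X ≥ r) at 30 % | Meets 0.0005? | Power at 65 % |
|---|---|---|---|---|
| 14 | 10 | 0.00167 | no | – |
| 14 | 11 | 0.00025 | yes | 22.0 % |
| 15 | 11 | 0.00067 | no | – |
| 15 | 12 | 0.00009 | yes | 17.3 % |

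The n = 15 power, term by term for k = 12 to 15, is 0.1110 + 0.0476 + 0.0126 + 0.0016 = 0.173.

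Fleming's normal approximation at 0.0005 gives 34 % (n = 14) and 37 % (n = 15), also far from 80 %. The smallest exact design with 80 % power at 0.0005 has 34 patients and a cut-off of 20 (attained alpha 0.00045, power 82.6 %).

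**Step 3: does the planned analysis use 0.05 %?** The Wilson lower limit is [p̂ + z²/2n − z√(p̂(1−p̂)/n + z²/4n²)] / (1 + z²/n) with z = 1.96. For 8 of 14 it is (0.5714 + 0.1372 − 0.2933)/1.2744 = 0.326.

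| Responders | Lower limit, n = 14 | Lower limit, n = 15 |
|---|---|---|
| 7 | 26.8 % | 24.8 % |
| 8 | 32.6 % | 30.1 % |

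The interval in SAP 12.1 first excludes 30 % at 8 responders, which is the protocol's cut-off.

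**Step 4: if all 15 patients are evaluable.** With r = 8 the attained alpha is 0.05001, just above 0.05 (power 88.7 %). With r = 9 it is 0.0152 (power 75.5 %). The exact 5 % design at n = 15 therefore needs 9 responders.

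**The case against.** The strongest defence is that this is a stray per-cent sign. The same SAP section gives 0.05 as a proportion for the first cohort and says that the second calculation follows a similar approach. The protocol has 5 %, and at 5 % the 80 % power reproduces. Enrolment of 40 patients ended in June 2016 and the SAP is dated August 2017, so the slip cannot have affected the sample size. All of this stands, and it limits the weight of the point. It does not make the printed sentence correct.

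A reader might infer more: that 0.05 % is the only decision level the SAP holds for this cohort, that 11 of 14 responders would be required, and that an effective regimen would be missed about four times in five. The documents do not support that. SAP section 8 sets a general level of 0.05, section 12.1 plans a 95 % Wilson interval for each dosing schedule, and no analysis section, planned table or addendum text uses 0.05 %. The 11-of-14 threshold describes a literal reading of the sample-size paragraph and no planned analysis.

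Nor is the number 15 an error in itself. The protocol also speaks of 15 additional patients of whom 14 complete, and the SAP does not say that its power was computed on 15.

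**Conclusion.** The point holds as a minor correction. SAP section 5 misstates the second cohort's one-tailed alpha by a factor of 100, and at the printed level the paired power would be 17.3 % (n = 15) or 22.0 % (n = 14), not 80 %. The 80 % is right at 5 % with the protocol's 8-of-14 rule, so the error lies in the unit of alpha. It corrects a stated design figure. It does not show a changed analysis or result.

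The figures rest on exact binomial tails at 30 % and 65 %. The protocol compared here is version 3.1, while the SAP's reference list names version 2. The mismatch between alpha and power is internal to the SAP and does not depend on that.

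**What to change.** Replace the end of the second-cohort sentence in SAP section 5, or correct it by addendum, with:

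> one-tailed alpha of 5 % (0.05); H0 rejected if at least 8 of 14 completed patients respond (protocol 8.2), attained alpha 3.1 %, power 81.6 % at p1 = 65 %.

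Do not add an 8-of-15 rule. The protocol contains none, and its attained alpha of 5.001 % exceeds the stated 5 %. If all 15 patients are evaluable, state that the exact 5 % design requires at least 9 of 15 (attained alpha 1.5 %, power 75.5 %). Present this as a property of the cited design, because the 2018 addendum shows that an initial analysis had already been run. Add that the Wilson lower limit at 8 of 15 is 30.1 %, so at that one count the interval and the exact design would disagree.

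The cost is a sentence or two of text, with no patients, data or re-analysis.

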8 BIOSTATISTICS

8.1 Trial Design and Hypotheses

This is a single-arm trial to evaluate efficacy of Selinexor in patients with relapsed/ refractory AML by complete response rate (CR) or CRi), as defined by the revised recommendations of the International Working Group for diagnosis, standardization of response criteria in Acute Myeloid Leukemia for AML.

The trial tests the null hypothesis that the observed response rate is less or equal than the predefined limit of 30% versus the alternative hypothesis that the response rate is at least 60%.:

$$H_0 : p \leq p_0 \text{ against the alternative hypothesis } H_1 : p \geq p_1.$$

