13.3 Other safety variables

Vital signs (blood pressure, heart rate, temperature) will be summarized with descriptive statistics by visit and dosing group. In addition, the changes from baseline values will be given. The changes from baseline will be analyzed by ANOVA method if feasible. Physical examination, ECG and ECOG results will be summarized with frequency tables.

14 Completion and premature discontinuation

Completion and premature discontinuation will be listed. The reasons for premature discontinuation will be presented.

15 Deviations from the analyses planned in the study protocol

The primary hypothesis of the study was clarified in the Statistical Analysis Plan compared to the definition in the protocol.

16 Execution of statistical analyses

Statistical analyses will be performed by 4Pharma Ltd.

17 Hardware and software

Statistical analysis, tables and patient data listings will be performed with SAS[®] version 9.3 for Windows (SAS Institute Inc., Cary, NC, USA).

18 References

Clinical Study Protocol, Final Protocol, Version 2 (25.08.2015)

19 Appendices

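### The SAP states the primary hypothesis on the observed response rate instead of the true rate, and carries over neither the protocol's 12-of-25 rule nor any named test

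*SAP*

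**What the plan says.** **SAP.** Section 6 gives the null as "The observed response rate is less or equal than 30" % and the alternative as "The observed response rate is over 30" %. Section 15 lists this as the one departure from the protocol: "The primary hypothesis of the study was clarified in the Statistical Analysis Plan compared to the definition in the protocol". Section 5 keeps the Fleming/A'Hern design inputs (p0 = 0.30, p1 = 0.60, one-tailed alpha 0.05, beta 0.10, 25 patients) but not the critical numbers. Section 12.1 plans the response rate with a Wilson 95% interval, overall and by dosing schedule, and names no test. Section 8 has a generic significance level of 0.05, two-sided unless stated otherwise. The 2018 addendum, written to clarify the primary analysis, adds no test of the rate against 30% and no cut-off.

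**Protocol.** Section 8.1 says in words: "The trial tests the null hypothesis that the observed response rate is less or equal than the predefined limit of 30" %, against "the alternative hypothesis that the response rate is at least 60" %. The line below puts the same pair in symbols as p ≤ p0 against p ≥ p1. Section 8.2 rejects the null at 12 or more of 25 and adds that "at least 12 responders should be observed to show the efficacy as postulated". For the 15 additional patients it uses 8 responders out of 14 completed patients. Section 8.4.1 makes every test descriptive except the one on the responder rate.

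**The concern.** The responder rate is the trial's only confirmatory test, so the hypothesis and its decision rule fix what the trial may conclude. A statement about the observed rate has no error probability attached: once the data are in, it is true or false by inspection. The SAP presents this wording as the clarified hypothesis and leaves out the number that turned the protocol's hypothesis into a decision. Someone working from the SAP alone therefore finds no primary success criterion except the literal one, an observed rate over 30%.

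For results of 8 to 11 out of 25, that literal reading and the protocol's rule give opposite answers.

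There is a smaller wording fault in the protocol. Its alternative starts at 60%, so true rates between 30% and 60% fall under neither hypothesis. Its remark about showing the postulated efficacy could also be taken to mean that 12 responders are evidence for 60%.

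**Working it through.** **Inputs.** p0 = 0.30, p1 = 0.60, one-sided alpha 0.05, beta 0.10, N = 25, critical number 12 (Protocol 8.2); 8 of 14 for the additional cohort (Protocol 8.2); Wilson 95% interval (SAP 12.1). X is the number of responders, binomial(n, p).

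**1. Reproduce the protocol's rule.**
- Fleming cut-off: 25 × 0.30 + 1.645 × √(25 × 0.30 × 0.70) = 7.5 + 3.77 = 11.27. The nearest integer is 11, and adding 1 gives 12.
- Exact alpha: P(X ≥ 12 | 25, 0.30) = 0.0442. At 11 it would be 0.0978.
- Exact power: P(X ≥ 12 | 25, 0.60) = 0.922.
- A search over n = 10 to 39 for exact alpha ≤ 0.05 and power ≥ 0.90 gives n = 25 with 12 responders as the smallest design. The stated design is reproduced.

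**2. The SAP's alternative read literally.** The smallest count with an observed rate above 30%, and its probability at a true rate of 30%:

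| n | Smallest count | Observed rate | P at p = 0.30 |
|---|---|---|---|
| 25 | 8 (7/25 = 28%) | 32% | 0.488 |
| 15 | 5 (4/15 = 26.7%) | 33.3% | 0.485 |
| 14 | 5 (4/14 = 28.6%) | 35.7% | 0.416 |
| 40 | 13 (12/40 = exactly 30%) | 32.5% | 0.423 |

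For n = 25, the chance of landing where the two readings disagree (8 to 11 responders) at a true rate of 30% is 0.488 − 0.044 = 0.444.

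**3. What the planned Wilson interval would say.** With z = 1.96, the limits are [p̂ + z²/2n ± z√(p̂(1 − p̂)/n + z²/4n²)] / (1 + z²/n).
- 8/25: 17.2% to 51.6%, which includes 30%.
- 11/25: lower limit 26.7%.
- 12/25: (0.48 + 0.0768 ± 1.96 × √(0.009984 + 0.001537)) / 1.1537 = 0.4827 ± 0.1824, that is 30.03% to 66.5%.

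So a lower Wilson limit above 30% is first reached at 12/25, the protocol's own cut-off.

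**4. The additional cohort.**
- 8/14: alpha 0.0315; power 0.816 at 65% and 0.907 at 70%, which agrees with the stated 80% and 90%.
- 8/15: alpha 0.05001, just over 5%.
- 9/15: alpha 0.0152; power 0.755 at 65% and 0.869 at 70%.

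If all 15 patients are analysed, the exact 5% rule therefore needs 9. A Wilson lower limit above 30% would already be met at 8/15, so the two rules differ there.

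**5. What 12/25 supports.** The observed rate is 48%, and the exact one-sided 95% lower limit is 30.5%. The rule is met with probability 26.8% at a true rate of 40%, 45.7% at 45% and 65.5% at 50%. Evidence that the true rate exceeds 60% at one-sided 5% would need 20/25: P(X ≥ 20 | 25, 0.60) = 0.029, against 0.074 for 19.

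**The case against.** The strongest reply is that the intention is clear. The SAP keeps a one-tailed alpha of 0.05 for the 25-patient design, describes its null as something to be tested, sets a 0.05 significance level and plans a Wilson interval. On those elements 8/25 does not succeed: its interval covers 30% and its one-sided p-value is 0.49. The protocol's symbols show that p was meant, and the SAP has repeated the protocol's loose word. This stands, and it rules out the stronger reading that a reader might draw from the 48.8%, namely that the SAP has abandoned 5% error control. No document says that 8/25, or 13/40, counts as success.

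The reply also covers most of the complaint about the protocol's alternative. SAP section 6 already moves it to above 30%, and section 15 says that the hypothesis was changed. Protocol 8.2 uses p1 as a design level. A critical proportion of 48% lying between 30% and 60% is normal for this kind of design, and the rejection probabilities at 40% to 50% are ordinary points on a power curve. A reader might infer that the sponsor plans to report a rate of at least 60% after 12 responders; no passage says so.

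The reply does not supply the missing rule. The SAP never links the Wilson interval or the 0.05 level to the 30% null, gives no critical number, and has a two-sided default in section 8 beside a one-tailed design in section 5. An evident intention is not a stated criterion for the only confirmatory test.

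**Conclusion.** The point holds as a mis-stated hypothesis with a missing decision rule. The wording on the observed rate is wrong in SAP 6 and in the verbal null of Protocol 8.1, and the SAP lacks the 12/25 rule and any named test. The literal reading (8/25, 48.8% at a true rate of 30%) and the protocol's rule (12/25, alpha 4.4%, power 92.2%) are four responders apart. The 48.8% measures how far the text departs from the design; it is not an operating characteristic that the sponsor has planned. The protocol's alternative of at least 60% is a lesser matter: rejecting the null supports a rate above 30% and nothing higher.

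This assumes independent patients with a common response probability within each cohort, and denominators of 25 and 14 or 15. Neither document gives a critical number for the pooled 40, so the pooled figure only illustrates the literal reading. SAP section 18 cites protocol version 2, whereas the protocol at hand is version 3.1; whether version 2 worded section 8.1 the same way cannot be checked.

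**What to change.** - In SAP 6 and Protocol 8.1, write H0: p ≤ 0.30 against H1: p > 0.30, where p is the true CR/CRi probability, tested at one-sided alpha 0.05.
- In the SAP, state that H0 is rejected for the 25-patient cohort at 12 or more of 25, noting that this is also where the Wilson 95% lower limit first exceeds 30%.
- For the additional cohort, restate the protocol's 8 of 14 completed patients (exact alpha 3.1%). Add that 9 of 15 is required if all 15 are analysed, because 8/15 gives 5.001%.
- Keep 0.60 only as the alternative used for power.
- In Protocol 8.2, change the end of the sentence on 12 responders so that the count serves to reject a true rate of 30% or less.

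The cost is a few words in each document, with no new data and no change of design. The 12/25 and 8/14 numbers already stand in the protocol, so restating them introduces no new threshold. The permitted claim becomes slightly weaker: above 30%, not at least 60%. If all 15 additional patients are analysed, needing 9 lowers the power at a true rate of 65% from 81.6% (8/14) to 75.5%.
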